At the University of Pennsylvania, we see approximately 20 cases of extremity STS per year. We anticipate that with the availability of proton radiotherapy, these numbers may increase. We estimate an annual accrual of 12 subjects per year for each cohort. We will also treat patients either preoperatively or postoperatively from Walter Reed Army Medical Center. In addition, this protocol will be listed on our web site as a formal protocol and information of its availability will be made known to treating professionals throughout our satellites as well as other referring physicians. These patients, if treated preoperatively with radiation therapy, will be required to have their surgery at the Hospital of the University of Pennsylvania.

Early Withdrawal of Subjects

When and How to Withdraw Subjects?

Recurrent or Progressive Disease: Subjects who have clinical or radiologic evidence of recurrent disease will undergo an evaluation to document the nature of the abnormality. If recurrent or progressive cancer is diagnosed, the subject will be considered off study at that time.

Subject Participation: Subjects may be withdrawn if the subject decides to refuse continuation of treatment or follow-up. Subjects may also be withdrawn for non-compliance with the protocol or withdrawal of consent. The reasons for withdrawal will be documented.

PI Decision: Subjects may be withdrawn at any time during the study if the PI believes it is in the subject's best interest. In this event, the reasons for withdrawal will be documented.

Once the subject has discontinued treatment, the primary reason for discontinuing treatment must be clearly documented in the subject's records and on the CRF. The investigator will assess each subject for response at the time of withdrawal.

Every effort will be made to follow subjects off study for toxicity and survival. Survival will be followed for a minimum of 5 years by means of scheduled appointments and available medical records. Every effort will be made to follow for overall survival.

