5 STUDY PROCEDURES

	Pre-treat	Day of F18-EF5 PET/CT Prior to injection	Weekly during RT	Visit prior to surgery	30 days post surg/RT ^{1*}	Q3 months for 2 years, then q6 months for years 3 - 5 after surgery/RT	Yearly (as long as the patient wishes to be followed)
Tests and Observations							
History and PE	X		X	X	X	X	X
ECOG PS	X						
Biopsy	X						
Urine Pregnancy Test		X ²					
Toxicity Assessment	X		X			X	
Tumor Measurement	X ¹			X		X	
18F-EF5 PET Scan (optional)	X ³						

1- *Post radiation/surgery follow-up schedule defined for each cohort in Section 6.

2- Urine pregnancy test is routinely performed prior to PET/CT scanning as departmental standard.

3 – Subjects may participate in study with or without performing 18F EF5 PET scan. This is a subject option.

Post-treatment Evaluation and follow-up

All subjects will be evaluated prior to initiation of treatment and weekly during the course of radiotherapy. For patients receiving pre-operative radiation, a visit will occur prior to surgery. This visit will involve an interval history and physical. All patients will be seen for a first post-operative/post-radiation office visit with either the attending radiation oncologist or surgeon no more than 30 days following surgery/radiotherapy or discharge from the hospital, whichever comes later. Pre-operative patients will be seen after surgery, weekly x 1 month, then every 2nd week x 1 month, then monthly for 3 months. Post-operative patients will be seen one month after surgery and then in 3 months. Follow up visits for pre-operative and post-operative patients will be with either the attending surgeon or radiation oncologist every 3 months for two years, and every 6 months thereafter for 3 years. These office follow-up visits will consist of an interval history and physical and imaging studies as clinically indicated. The wound complication endpoint will be scored at 4 months after surgery in the pre-operative group. Post-operative patients will be scored for fibrosis, edema and joint stiffness within 2 years after after radiation.

Assessment of Tumor Response

Tumor Response (RECIST criteria): RECIST criteria will only be evaluated after radiation just prior to surgery in the pre-operative patients. Post-operative patients will not be evaluated since they undergo complete resection of STS.

Target Lesions:

- **Complete Response (CR):** Disappearance of all target lesions.

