- **Partial Response (PR):** At least a 30% decrease in the sum of the longest diameters of target lesion, taking as reference the baseline sum of the longest diameters.

CONFIDENTIAL

- **Progressive Disease (PD):** At least a 20% increase in the LD of the target lesions, taking as reference the smallest sum of the LD recorded since the treatment started or the appearance any new lesion(s)
- **Stable Disease (SD):** Neither sufficient shrinkage to qualify for PR nor sufficient increase to qualify for PD, taking as reference the smallest sum LD since the treatment started.

Non-Target Lesions:

- **Complete Response (CR):** Disappearance of all non-target lesions and normalization of tumor marker levels.
- **Incomplete Response/Stable Disease (SD):** Persistence of one or more non-target lesion(s) and/or maintenance of tumor marker levels above normal limits.
- **Progressive Disease (PD):** Unequivocal progression of existing non-target lesions or any new lesion(s)

Confirmation of Response (used only for studies with response as primary endpoint)

- To assign a PR or CR, changes in tumor measurement must be confirmed by repeat assessments no less than 4 weeks after the criteria for response are first met. (*Reflect this in your study procedures table in section 6*)
- To assign SD, measurements must have met the stable disease criteria at least once after study entry at "X" interval (*as defined by protocol*).

Failure

- **Local failure** is defined as: evidence of tumor growth in any direction beyond that present of the pre-treatment imaging studies or the appearance of tumor in tissues previously scored as sites of subclinical disease. The imaging studies are to be comparable in technical factors.
- **Marginal failure** is defined as appearance of tumor growth at the margin of the target volume
- **Nodal Failure:** Failure in regional lymph nodes.
- **Distant failure** is defined as appearance of tumor at sites beyond regional nodal and marginal site.
- **Progression-Free Survival:** duration measured from first day of treatment to first documented failure, death due to any cause or last patient contact alive.
- **Overall Survival:** Duration measured from first day of treatment until death due to any cause or last patient contact alive.
- Time to local failure, time to distant failure, PFS and OS will be calculated from **first day of radiation** in the pre-operative patients and calculated from **day of surgery** in the post-operative patients.

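### The local-failure definition has no growth threshold, so a pre-operative tumor that grows by less than 20% before its planned resection is both RECIST stable disease and a PFS event

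*Combined protocol and SAP*

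**What the plan says.** The Failure list in Section 5 (Study Procedures) defines local failure as "evidence of tumor growth in any direction beyond that present of the pre-treatment imaging studies". A second limb covers new tumor in tissue earlier judged to hold only subclinical disease, and a further sentence asks for technically comparable scans. The list gives no minimum amount of growth and does not exempt a tumor that is still in place before its planned operation.

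The same list defines PFS as "duration measured from first day of treatment to first documented failure, death due to any cause or last patient contact alive". Section 5 and Section 6.1 (Clinical Efficacy) both start the pre-operative clock for time to local failure and PFS on the first day of radiation.

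The Target Lesions list, also in Section 5, sets the RECIST thresholds:

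- Progressive disease: "At least a 20% increase in the LD of the target lesions", measured against the smallest value since treatment began, or a new lesion.
- Partial response: "At least a 30% decrease in the sum of the longest diameters of target lesion".
- Stable disease: "Neither sufficient shrinkage to qualify for PR nor sufficient increase to qualify for PD".

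On timing, Section 5 says that "RECIST criteria will only be evaluated after radiation just prior to surgery in the pre-operative patients". Its schedule table marks a tumor measurement at the visit before surgery.

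The analysis text in Sections 6.1 and 6.3 refers to time to local recurrence, a term the protocol never defines. Section 2 (Early Withdrawal of Subjects) says: "If recurrent or progressive cancer is diagnosed, the subject will be considered off study at that time".

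**The concern.** In the pre-operative cohort the tumor stays in place through radiation and the wait for surgery, and it is measured again at the end of that period. Two rules in the same section apply to that one measurement. The response rule tolerates growth of up to 20%; the failure rule tolerates none. One patient can therefore appear as stable in the response table and as a failure on the PFS curve at the same visit.

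At stake is what the pre-operative PFS estimate means. An increase too small to count as progression under RECIST, in a tumor about to be removed, would carry the same weight as a relapse or a death. The same events would enter the exploratory analyses relating EF5 signal to PFS. Local control would be affected too if local recurrence in the analysis sections is taken to mean local failure as defined in Section 5.

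**Working it through.** The plan gives no figure for growth before surgery, so there is none to reproduce. The check sets its rules side by side.

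**Inputs**

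- Local failure: any growth beyond pre-treatment imaging (Section 5, Failure).
- RECIST: partial response at a 30% decrease or more, progression at a 20% increase or more or a new lesion, stable disease in between (Section 5, Target Lesions).
- Start of the pre-operative clock: first day of radiation (Sections 5 and 6.1).
- Radiation: 5-6 weeks (Section 6.1). Interval to surgery: 4-12 weeks (Sections 4 and 6.1).
- Evaluable pre-operative patients: 40 (Section 6.4).

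**Step 1: time at risk with the tumor in place.** Shortest: 5 + 4 = 9 weeks. Longest: 6 + 12 = 18 weeks. All of it falls after the clock starts. In the post-operative cohort the clock starts on the day of surgery.

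**Step 2: classify one measurement under both rules.** Change = (new diameter − pre-treatment diameter) / pre-treatment diameter. I assume that no smaller value was recorded in between, so both rules use the pre-treatment scan as reference. For example, growth from 100 mm to 105 mm is (105 − 100)/100 = 5%.

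| Change in longest diameter | RECIST | Failure list, read literally |
|---|---|---|
| −31%, −30% | Partial response | No growth in this diameter |
| −29%, −10%, 0% | Stable disease | No growth in this diameter |
| +1%, +5%, +10%, +19% | Stable disease | Local failure and PFS event |
| +20% | Progressive disease | Local failure and PFS event |

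By longest diameter, the rules conflict only above 0% and below 20%. Because the failure rule counts growth in any direction, a tumor that grows in another dimension could also conflict without its longest diameter increasing.

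**Step 3: look for text that resolves the conflict.** The requirement for comparable scans reduces technical differences but sets no threshold. Section 6.1 repeats the PFS rule and clock starts without narrowing what a failure is.

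**Step 4: test the definition after resection.** A recurrence inside the former gross tumor volume that is smaller than the original mass is not growth beyond the pre-treatment scan. The second limb covers subclinical sites, whereas Section 3 defines that volume as gross disease. Read literally, such a recurrence could go uncounted, so the definition needs a separate post-resection part.

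**Step 5: size per patient.** With 40 patients in the denominator, one patient in the conflict zone who would otherwise have no event adds 1/40 = 2.5 percentage points to the crude PFS event proportion. If that patient later fails in any case, only the event date changes.

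**The case against.** The strongest reply is that the definition asks for evidence of tumor growth on comparable imaging. A 5 mm difference on a 100 mm mass need not be such evidence, and an investigator may decline to call it failure. That is fair as a description of sensible practice, and the documents do not say that swelling or measurement error must be scored as failure. But the judgment is left to each assessor without a threshold, so the reply does not remove the conflict.

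Several stronger readings are tempting and should be resisted.

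- *Every patient with stable disease is an event.* Stable disease also includes no change and shrinkage of less than 30%, which are not failures unless another dimension grew.
- *Such patients leave the study before surgery and weaken the wound-complication test.* Section 2 requires an evaluation and a diagnosis of recurrent or progressive cancer, and does not refer to the local-failure definition. It still asks for follow-up for toxicity and survival. Evaluability depends on 4 months of follow-up after surgery, and up to 50 patients may be enrolled to reach 40. No effect on the primary endpoint is shown.
- *Local control will fall short of the 90% quoted in the introduction.* No test against that figure and no comparison between cohorts is planned. The analyses speak of local recurrence, which a tumor not yet resected has arguably not had, and the documents do not settle which meaning applies.
- *The post-operative definition fails as well.* The second limb can apply to the resection bed and the first to gross residual disease.

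It also stands that the affected endpoints are secondary, estimated by stratum with Kaplan-Meier curves, and that the EF5 analyses are exploratory.

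**Conclusion.** The concern holds for pre-operative tumors that grow before resection by more than 0% and less than 20% in longest diameter. Read literally, the protocol makes each of these patients stable disease and a local-failure and PFS event dated before surgery, whatever follows. Only the effect on PFS is certain. An effect on local control depends on reading local recurrence as local failure.

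The total size is unknown because the documents give no rate of growth before surgery. The only figure they support is the 2.5 points per otherwise event-free patient, which assumes a denominator of 40. The conclusion rests on a literal reading of the Failure list and on the pre-treatment scan being the reference for both rules. It deserves correction because a stated rule gives an unintended result and the remedy is cheap. It does not call the primary endpoint or its power into question.

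**What to change.** In the Failure list of Section 5 and the Clinical Efficacy paragraph of Section 6.1, split the definition for the pre-operative cohort by timing:

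- Before resection, growth of the tumor in place counts as an event for time to local failure and PFS only if it meets the RECIST progression definition already in Section 5.
- After resection, local failure is reappearance of tumor in the operated or irradiated site, including the former gross tumor volume.

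Use one term, local failure or local recurrence, in Sections 5, 6.1 and 6.3, including the EF5 analyses. Do not extend RECIST progression to the post-operative cohort, which Section 5 says will not be evaluated by RECIST.

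The protocol team should also reconcile the reference to progressive cancer in Section 2, and the one to disease progression in the late-toxicity paragraph of Section 6.1, with the revised endpoint definition. This is a request for consistent terms; who leaves the study is for the protocol team to decide.

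The cost is a wording amendment that uses measurements already scheduled, best made before outcomes are scored so that the choice cannot depend on the data. The downside is that true growth below 20% before surgery is not counted as an event. For a spherical tumor (an assumption), that limit corresponds to just under 1.2³ − 1 = 0.728, or about 73%, in volume.

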Publishers, 1964). Patients will be assessed for fibrosis, joint stiffness and edema within 2 years of completion of radiotherapy.

Clinical Efficacy is defined for pre-operative patients as overall response rate (CR + PR according to RECIST criteria) which is scored after radiation and before surgery. Progression-Free Survival is defined from first day of treatment to first documented failure, death due to any cause or last patient contact alive. Overall Survival is defined from first day of treatment until death due to any cause or last patient contact alive. Time to local failure, time to distant failure, PFS and OS will be calculated from first day of radiation in the pre-operative patients and calculated from day of surgery in the post-operative patients.

Rules for Early Termination for Feasibility, Acute Toxicity and Wound Complication:

Bayesian probability calculations will be employed to define rules of early termination and end of trial evaluation for feasibility and safety. The tables below indicate termination rules after groups of 3 patients have been treated. Hundreds of patients with certain types of cancer have undergone radiation therapy with protons. Thus, we will assume some "prior" feasibility and safety data for protons delivered at the standard radiation dose for our Bayesian calculations. We will assume prior information equivalent to that of 6 treated patients, which is commonly required to establish feasibility and safety in a standard 3+3 phase I trial design.

Feasibility – conducted separately for each stratum

We will assume a beta (5,1) prior, which is information equivalent to feasibility established in 5 of 6 treated patients. A feasibility rate > 90% is considered acceptable. If the number of patients deemed feasible is less than or equal to the number in the table below then termination will be considered as it is highly unlikely that the feasibility rate is > 90%, as noted by the Bayesian posterior probabilities.

Bayesian Rule for Feasibility				
Patients treated	3	6	9	12
Patients who are feasible	1	4	6	9
Posterior Prob[feasibility rate >90%]	0.0	0.0	0.0	0.0
Action	Terminate enrollment			

Acute Toxicity – conducted separately for each stratum * excludes wound complication *

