6.2 PHASE II STUDY

Design and Objectives:

This stratified phase II trial is designed to evaluate early complications (e.g., wound complication in pre-operative patients) and late complications (e.g., fibrosis, joint stiffness and edema in post-operative patients). Patients with STS of the lower extremity only will be treated in the phase II study. Justification for enrolling lower extremity STS in phase II is that 80% of STS patients treated in the Department of Radiation Oncology have lower extremity STS and they are the subgroup who may benefit most from protons. For example in the study by O’Sullivan et al (Lancet 359, 2002), in pre-operative patients, the wound complication rate from photon radiotherapy in patients with lower extremity STS was 43% (30 events in 70 patients) compared to 5.5% (1 event in 18 patients) in upper extremity STS. 40 evaluable patients (including evaluable patients from the feasibility stage) will be enrolled in each stratum.

Endpoints:

Same endpoints as in Section 6.1: Wound complication, Fibrosis and joint stiffness, Edema, Acute toxicity, Late toxicity and Clinical Efficacy.

Evaluable for analysis:

For pre-operative patients, patients must have a minimum of 4 months of follow-up post-surgery to be evaluable and included in the phase II analysis. For post-operative patients, patients must have a minimum of 2 years of follow-up from the end of radiotherapy to be evaluable and included in the phase II analysis.

Rules for Early Termination for Wound Complications:

We will assume a beta (2,4) prior, which is information equivalent to wound complication in 2 of 6 treated patients. A wound complication rate >40% is considered unacceptable. If the number of patients with wound complications is greater than or equal to the number in the table below then termination will be considered as it is likely that the wound complication rate is >40%, as noted by the Bayesian posterior probabilities.

Bayesian Rule for Wound complication						
Patients treated & followed 4 months	1	2	2	3	3	4
Patients who experience wound complication	5	0	5	0	5	0
Posterior Prob[wound complication toxicity rate >40%]	8	1	1	1	1	1
		1	3	5	7	9
	0	0	0	0.	0.	0.
	.	.	.	8	7	7
	7	8	8	1	9	8
	6	5	2			
Action	Terminate enrollment					

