6.3 STATISTICAL ANALYSES

Pre-operative patients: Toxicity data will be graded and tabulated. A one-sample one-sided chi-square test will be performed to test the null hypothesis that the wound complication rate is 45% (same as photon). Patients must have a minimum of 4 months of follow-up after surgery to be evaluable for this analysis.

CONFIDENTIAL

This material is the property of the University of Pennsylvania. Do not disclose or use except as authorized in writing by the study sponsor

Post-operative patients: Toxicity data will be graded and tabulated. In the study by Davis et al (Radiother and Oncol 75, 2005), the grade 2+ fibrosis rate was 48%, joint stiffness 23% and edema 23%. Since fibrosis is the most common post-operative toxicity, it is considered the primary endpoint and a one-sample one-sided chi-square test will be performed at the 5% significance level to test the null hypothesis of 50% (same as photon). Joint stiffness and edema are less frequent toxicities and will be treated as secondary endpoints. The null hypothesis is that the grade 2 or higher rate is 25% (same as photon) for these endpoints. Patients must have a minimum of 2 years of follow-up after surgery to be evaluable for this analysis.

Acute toxicity (Late toxicity): Toxicities will graded and tabulated by stratum.

Clinical Efficacy: For pre-operative patients, the RECIST response rate (CR + PR based on RECIST) and 90% exact CI will be computed. For each stratum, time to local recurrence, time to distant recurrence, PFS and OS will be estimated by Kaplan-Meier analysis.

Exploratory Analyses of [¹⁸F]-EF5:

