With 12 patients per year enrolled to each stratum and accounting for required follow-up time for feasibility and toxicities, this study should be active for 7 years. Twelve pre-operative and 12 post-operative patients will be enrolled on the feasibility portion of the trial. If feasibility and safety are acceptable then 40 evaluable pre-operative patients and 40 evaluable post-operative patients with STS of the lower extremity (each group includes evaluable patients from the feasibility stage) will be enrolled in the phase II portion of the trial. Up to 50 pre-operative patients may need to be enrolled to yield 40 evaluable patients with lower extremity STS who undergo surgery and have 4 months of follow-up post-surgery. With 40 evaluable patients, there will be 84% power for a chi-square test at one-sided 5% type I error to test a grade 2 or higher wound complication rate of 45% versus an alternative rate of 25%.

Similarly, up to 50 post-operative patients may need to be enrolled to yield 40 evaluable patients with lower extremity STS who receive post-operative radiotherapy and remain on-study for 2 years from the end of radiotherapy. With 40 evaluable patients, there will be 83% power for a chi-square test at one-sided 5% type I error to test a grade 2 or higher fibrosis rate of 50% versus an alternative rate of 30%. In addition, there will be 80% power for chi-square tests at one-sided 2.5% type I error to test grade 2 or higher joint stiffness and

CONFIDENTIAL

edema, each with rates of 25% versus alternative rates of 9%. These secondary analyses will be tested at a 2.5% significance level, to control the overall type I error.

All correlative analyses of hypoxia and clinical outcome are exploratory. Results from this unique study will be used to estimate the magnitude of the associations for both RECIST response and time-to-event outcomes and will provide important guidance for future studies of the prognostic importance of hypoxia in STS patients.

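### Read literally, the Phase II evaluability rule in Section 6.2 restricts the OS and PFS analyses to patients selected for surviving, and no all-treated set is named for them

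*Combined protocol and SAP*

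**What the plan says.** Section 6.2 gives the Phase II endpoints as "Same endpoints as in Section 6.1: Wound complication, Fibrosis and joint stiffness, Edema, Acute toxicity, Late toxicity and Clinical Efficacy". Section 6.1 defines Clinical Efficacy to include PFS and OS. The next paragraph of Section 6.2, Evaluable for analysis, is the only Phase II analysis-set rule. Pre-operative patients need a "minimum of 4 months of follow-up post-surgery to be evaluable and included in the phase II analysis", and post-operative patients a "minimum of 2 years of follow-up from the end of radiotherapy to be evaluable and included in the phase II analysis". Section 2 carries the same minimums. Section 6.4 describes the 40 evaluable post-operative patients as those who receive radiotherapy and "remain on-study for 2 years from the end of radiotherapy".

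Under Clinical Efficacy, Section 6.3 says: "For each stratum, time to local recurrence, time to distant recurrence, PFS and OS will be estimated by Kaplan-Meier analysis". It names no population. In the post-operative toxicity paragraph the same section says: "Patients must have a minimum of 2 years of follow-up after surgery to be evaluable for this analysis". That is narrower in scope than Section 6.2, and it counts the 2 years from surgery instead of from the end of radiotherapy.

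OS runs to death or last contact ("Duration measured from first day of treatment until death due to any cause or last patient contact alive"). Time zero is the first day of radiation in the pre-operative stratum; in the post-operative stratum times are "calculated from day of surgery in the post-operative patients".

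**The concern.** A minimum-follow-up condition is understandable for an endpoint scored at a fixed time, such as wound complication at 4 months or fibrosis within 2 years. It is not neutral for survival. A post-operative patient who dies 10 months after radiotherapy does not have 2 years of follow-up, so the rule removes that patient from the set in which OS is estimated. The set is then selected on the outcome, and the Kaplan-Meier curve is flat at 100% until the condition has been met. Every later estimate is conditional on having survived that long. The bias always favours the treatment.

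Local control, PFS and OS are stated secondary objectives for both phases. Section 6.1 expects the feasibility-stage efficacy analyses to be done in the Phase II stage, so no all-treated survival analysis is specified elsewhere. If the wording stays open to two readings, the population could be settled after the data are known.

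**Working it through.** **The plan's own figures.** The documents state no survival figure. The figures tied to the evaluable set are the power statements in Section 6.4. For a one-sided, one-sample test with n = 40, power = Φ[(|p0 − p1| − 1.645·√(p0(1−p0)/n)) / √(p1(1−p1)/n)].
- Wound, 45% v 25%: (0.20 − 1.645 × 0.0787)/0.0685 = 1.03, power 84.9% (stated 84%).
- Fibrosis, 50% v 30%: (0.20 − 1.645 × 0.0791)/0.0725 = 0.97, power 83.3% (stated 83%).
- Enrolment: 40/0.80 = 50, as stated.

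These concern the primary tests, and the choice of survival population does not change them.

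**Period with no possible death, post-operative (clock from surgery).**
- Surgery to radiotherapy: 3 to 8 weeks (Section 4).
- Radiotherapy: 7 to 8 weeks. Section 3 gives 63 to 72 Gy(RBE) at 1.8 per fraction, so 35 to 40 fractions, taken here as five a week; Section 6.1 says 8 weeks.
- Shortest: (3 + 7) weeks + 24 months = 2.3 + 24 = 26.3 months.
- Longest: (8 + 8) weeks + 24 months = 3.7 + 24 = 27.7 months.
- With the 2 years counted from surgery, as in Section 6.3: 24.0 months.

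Two-year OS is 100% in the evaluable set on either anchor.

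**Pre-operative (clock from first radiation).** Radiotherapy takes 5 to 6 weeks (Section 6.1) and surgery follows 4 to 12 weeks later (Section 4).
- Shortest: 9 weeks + 4 months = 6.1 months.
- Longest: 18 weeks + 4 months = 8.1 months.

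Patients who never reach surgery are excluded as well.

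**Size of the distortion.** The documents give no survival rates, so a constant hazard and the true 5-year rates below are assumptions. With S(t) = S5^(t/60), t in months:
- reported 5-year OS = S5 / S(t)
- share of 5-year deaths dropped = (1 − S(t)) / (1 − S5)

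For S5 = 70%, true 2-year OS is 0.70^0.4 = 86.7%. At t = 26.3, S(t) = 0.855, so reported 5-year OS is 0.70/0.855 = 81.8%.

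| True 5-year OS | True 2-year OS | Reported 2-year, post-op | Reported 5-year, post-op (t = 24.0 / 26.3 / 27.7) | Deaths dropped, post-op (same t) | Reported 5-year, pre-op (t = 6.1 / 8.1) |
|---|---|---|---|---|---|
| 50% | 75.8% | 100% | 66.0 / 67.8 / 68.9% | 48 / 52 / 55% | 53.7 / 54.9% |
| 70% | 86.7% | 100% | 80.7 / 81.8 / 82.5% | 44 / 48 / 51% | 72.6 / 73.5% |
| 80% | 91.5% | 100% | 87.5 / 88.2 / 88.7% | 43 / 47 / 49% | 81.8 / 82.4% |

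A Kaplan-Meier simulation (50 patients, exponential survival, 1,000 runs, restriction at 2.25 years) agrees. With an assumed true 2-year OS of 80%, mean 5-year OS was 57% in all treated patients and 73% in the evaluable set.

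A bound from the plan's own enrolment figures: if all 50 − 40 = 10 anticipated losses in the post-operative stratum were deaths, a 2-year OS of 40/50 = 80% would be reported as 100%.

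**PFS and time to failure.** Early deaths leave these analyses in the same way. Early recurrences need not. Section 6.2 asks for follow-up, and a patient who recurs at 12 months and is still followed can reach 2 years.

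**The case against.** The strongest reply is that Section 6.3 is the operative analysis text and attaches the minimum only to the wound paragraph and the fibrosis, stiffness and edema paragraph. In the latter it reads "Patients must have a minimum of 2 years of follow-up after surgery to be evaluable for this analysis". The Clinical Efficacy and EF5 paragraphs carry no such condition. Section 2 (Early Withdrawal of Subjects) keeps following off-study patients for toxicity and for survival to at least 5 years, which would serve little purpose if early deaths were discarded. Section 6.1 keeps feasibility patients in follow-up for clinical efficacy with no evaluability test. Read literally, Section 6.2 would also drop acute toxicity in patients who die early and RECIST responses scored before surgery, which suggests it was written with the fixed-time tests in mind.

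Much of this stands: an all-treated survival analysis may well have been intended. But Section 6.2 speaks of the Phase II analysis as a whole directly below a list that includes Clinical Efficacy, and nothing exempts OS or PFS. Nor does the text favour reading the minimum as potential follow-up with early deaths retained, since Section 6.4 describes evaluable post-operative patients as those who "remain on-study for 2 years from the end of radiotherapy". The off-study follow-up shows that the data will exist; it assigns them to no analysis.

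Three stronger readings are tempting and not supported:
- **That survivor-only OS is the settled plan.** The sections conflict, so this is the consequence of one literal reading.
- **That early recurrences are necessarily lost from PFS.** That requires joining the phrase in Section 6.4, which belongs to an enrolment projection, to the rule in Section 2 that takes patients off study at recurrence.
- **That the EF5 models suffer a quantifiable loss of power.** The scan is optional, some post-operative patients may be referred after resection, the 2-year restriction could bear only on that stratum, and Section 6.4 calls these analyses exploratory.

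**Conclusion.** The point holds as a defect of specification that should be fixed. As worded, Section 6.2 admits to the survival analyses only patients who have met a follow-up minimum. Following it literally makes post-operative OS 100% to 26.3–27.7 months from surgery (24 months on the Section 6.3 anchor) and pre-operative OS free of deaths for 6.1–8.1 months from first radiation. Those periods rest on the protocol's own intervals, with five fractions a week assumed for the 7-week figure.

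The size of the bias rests on assumed survival. Over true 5-year rates of 50% to 80% with a constant hazard, 5-year OS is overstated by about 8 to 19 points post-operatively and 2 to 5 points pre-operatively. A different hazard shape would change these figures, but not the 100% at 2 years in the post-operative stratum.

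OS, PFS and local control are secondary and descriptive. No hypothesis test, sample size or stopping rule depends on them, and the primary tests keep their stated power.

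**What to change.** 1. In Section 6.2, limit the 4-month minimum to the wound complication test and the 2-year minimum to the fibrosis, joint stiffness and edema tests. Align Sections 2 and 6.4 with this.
2. Reconcile the two starting points for the 2 years: end of radiotherapy in Sections 2, 6.2 and 6.4, surgery in Section 6.3.
3. In Section 6.3, state that PFS, OS, time to local recurrence and time to distant recurrence use every patient who started protocol treatment in the stratum, from the defined time zero, with patients without an event censored at last contact. Apply the same rule to the EF5 time-to-event models, among scanned patients.
4. State that going off study at recurrence does not remove a patient from these analyses.
5. If results in 2-year survivors are wanted, report them separately as a labelled landmark analysis.

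The cost is wording. The plan already provides for survival follow-up off study, so no new data collection is needed. The survival estimates will be less favourable than under the literal rule.
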